The R21 phase of this project (PK Study: Study to Establish the Bioavailability and Pharmacokinetic Measures of *H. procumbens* Extract in Humans; Dosing Study: Study of Change in Systemic Inflammatory Markers after 4-Week Consumption of *H. procumbens* Extract by Humans) addresses the following objectives: (1) further define the bioavailability and short term pharmacokinetics of the principal secondary metabolites of a well-characterized aqueous-ethanolic extract of *H. procumbens* in non-enteric and enteric capsules; (2) define the biological signature and hypothetical mechanism of action of the *H. procumbens* extract in patients with knee osteoarthritis over four-week dosing; and, (3) develop protocol, data and safety monitoring plan and manual of operations/procedures and obtain all necessary regulatory approvals for the R33 phase. Following successful completion of the R21 phase, these objectives will be addressed during the R33 phase: (1) confirm and extend assessment of the impact of the *H. procumbens* extract upon the biological signature of the above referenced systemic inflammatory biomarkers and biomarkers in synovial fluid of patients consuming either of two doses over twelve weeks, as well as these markers in cultures of joint tissue; and, (2) evaluate the relationship between changes in systemic and local joint biomarker levels and clinical outcomes (pain, stiffness, functional difficulty). Completion of these studies will ensure that future clinical trials can be conducted with the methodological rigor and outcome measures needed to evaluate the effectiveness of such *H. procumbens* extracts.

FULL PROTOCOL TITLE

***Study to Establish the Bioavailability and Pharmacokinetic Measures
of H. procumbens Extract in Humans***

Study Chairman or Principal Investigator:

**[name]
Professor
Department of Biochemistry
University of Missouri
Columbia, Missouri;
[contact]; [contact]**

Supported by:

**The National Center for Complementary and Integrative Health Grant Number:
7R21AT009086-03 and the University of Missouri**

Study Intervention Product:

12.	COMMITTEES.....	34
13.	PUBLICATION OF RESEARCH FINDINGS.....	34
14.	REFERENCES.....	34
15.	SUPPLEMENTS/APPENDICES	37
I.	United States Patent – Harpagoside-enriched Extract from Harpagophytum procumbens and Processes for Producing Same	
II.	Biosketches – Study Team: [name] (Principal Investigator) [name] (Co-Investigator) [name] (Study Biostatistician)	
	DSMB: [name], [name] [name]	
III.	Letter of Support from the University of Missouri Heath Sciences Clinical Research Center	

STUDY TEAM ROSTER

[name] (Principal Investigator)
University of Missouri
Biochemistry Department
[name]
Columbia, Missouri 65211
[contact] (phone)
[contact] (fax)
[contact]

[name] (Co-Investigator)
University of Missouri Health Sciences Center
Department of Medicine, Division of Rheumatology-Immunology

Columbia, Missouri 65211
[contact] (phone)
[contact]

[name] Co-Investigator and Study Biostatistician
Division of Plant Sciences
[name]
University of Missouri,
Columbia Missouri 65211
[contact]

PARTICIPATING STUDY SITES

University of Missouri Health Sciences Center
Department of Medicine, Division of Rheumatology-Immunology
[name] (Co-Investigator)
Columbia, Missouri 65211
[contact] (phone)
[contact]

University of Missouri Health Sciences Clinical Research Center
[name]
[name], Medical Director
Columbia Missouri 65211
[contact]
[contact]
[contact]

PRÉCIS

Study Title: Study to Establish the Bioavailability and Pharmacokinetic Measures of *H. procumbens* Extract in Humans (PK Study)

Objectives

Primary Objective: To determine bioavailability and pharmacokinetic properties of harpagoside, harpagide, verbascoside, 8-p-coumarylharpagide and eicosanoids (product markers) after oral consumption of a daily dose of *H. procumbens* (i.e., capsules containing a total amount of extract yielding 100mg harpagoside) in patients with knee, hip, or hand osteoarthritis. We hypothesize that the pharmacokinetic properties of the *H. procumbens* aqueous - ethanolic extract as described in US Patent 6,280,737 B1 (Appendix 1; Example 2), will resemble the results obtained with healthy subjects without osteoarthritis, as reported by Loew et al.¹

Secondary Objective: Compare the bioavailability and pharmacokinetic properties after dosing with an enteric coated capsule to changes found after dosing with a non-enteric coated capsule. We hypothesize the C_{max} , t_{max} , and AUC values for product

markers will be enhanced by the cellulose (enteric) coating.

Design and Outcomes

A one-dose design will be used to measure bioavailability and pharmacokinetic properties of the *H. procumbens* study product, which is an aqueous extract enriched in harpagoside from which pro-inflammatory mediators have been removed by precipitation with ethanol, as described in U.S. Patent 6,280,737 B1. Dosing level for this study will be extract containing 100mg harpagoside, previously shown to be safe.^{2,3} Level of product markers will be measured for 24 hours following a single dose of *H. procumbens* study product, with blood collections taken at timed intervals.

Interventions and Duration

Dosing level for this study will be extract containing 100mg harpagoside (HP extract). Levels of product markers will be measured for 24 hours following a single dose of *H. procumbens* study product, with blood collections taken at timed intervals. Participants will be randomly assigned to receive HP extract in either enteric coated or non-enteric coated capsules.

Sample Size and Population

The study sample recruited into the study will consist of adults with knee osteoarthritis (n = 12 participants with complete data). Six of the participants will receive the HP extract in enteric coated capsules and the other six will receive the HP extract in non-enteric coated capsules.

The study size was determined based on a conservative estimate of the sample size needed based on the exemplar research used for comparison that used 6 healthy male volunteers.¹ We will balance both arms of the study with regards to sex (6 male and 6 female).

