3. STUDY DESIGN

Study Design - A one-dose randomized design will be used to measure bioavailability and pharmacokinetic properties of the *H. procumbens* study product, an aqueous extract enriched in harpagoside from which pro-inflammatory mediators have been removed by precipitation with ethanol, as described in U.S. Patent 6,280,737 B1 (HP extract). Dosing level for this study will be extract containing 100mg harpagoside, previously shown to be safe.^{2,3} Level of product markers will be measured for 24 hours following a single dose of HP extract, with blood collections taken at timed intervals.

Primary Outcomes – pharmacokinetic metrics:

C_{\max} (ng/mL) – first maximal concentration,

t_{\max} (h) – time to reach the C_{\max} ,

AUC (0-t) (ng/mL) – Area under the curve, and

Terminal $t_{1/2}$ (h) – terminal half-life.

Study Population - Adults with knee osteoarthritis (n = 12). Equal numbers of participants will be randomly assigned to receive study product in either enteric or non-enteric coated capsules.

Study Location - Participants will be recruited from MU Healthcare clinics that treat patients diagnosed with knee osteoarthritis. Participants will be treated at the University of Missouri Health Sciences Clinical Research Center (CRC). A letter of support from the Medical Director of the CRC is provided in the Appendix

Duration of Enrollment Period and Follow-up – Enrollment should be completed within 2 months after the final protocol is approved by the NIH, IRB and FDA. Each person enrolled in the study will be followed throughout the PK testing session and for the 24 hour period following the end of the testing session blood draw schedule.

Intervention and Administration - The study product will be packaged in either enteric or non-enteric capsules by [name], Pharm D, (MU-IDS Pharmacist). Participants will be randomly assigned to receive HP extract in either capsule type. At the PK testing session, all participants will receive capsules to deliver an oral dose of HP extract which provides 100mg of harpagoside.

Randomization, Blinding, and Stratification – Participants will be randomized to receive HP extract in either enteric coated or non-enteric coated capsules. Assignment to study group will be conducted double-blind. A pilot study indicated participants will not be able to distinguish between enteric and non-enteric capsules.

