6.2 Description of Evaluations

6.2.1 Screening Evaluation

The Screening Evaluation session to determine whether the patient is eligible to participate in the PK Study will occur from 2 to 14 days before the PK testing session. The Screening session will include the informed consent procedure and screening activities to ensure eligibility (described below).

Consenting Procedure

Prior to participants' participation in the study, written informed consent for the study, including screening and study procedures, will be obtained from each participant. CRC project staff or [name] will ensure that the participant is given full and adequate oral and written information about the nature, purpose, possible risk and benefit of the study. The participant's signed and dated informed consent will be obtained before conducting any study specific procedures. The CRC will store the original, signed Participant Informed Consent Form and a copy will be given to the participant.

Screening

Only volunteers who consent and pass all screening assessments will be scheduled for a PK testing session. Study participation will begin within 14 days of the Screening Evaluation session. At the screening session, the individual's SID number will be used to label all study data collected at the Screening session.

Following the completion of the informed consent procedures during the Screening session, a brief survey will be completed before other screening procedures are conducted. The survey will include items to record demographic information needed to describe the study sample (e.g., age, gender, race and ethnicity) and items to record contact information (e.g., address, phone number / email address).

The following eligibility screening evaluations will be completed.

- Medical history interview – Medical history will be collected via interviews. Participants will be asked about all previous diagnoses, allergies, procedures, and treatments to verify relevant inclusion/exclusion criteria (Section 4).
- Current medication use – Participants will provide a listing of all medications (prescription and over-the-counter) they are currently taking.. Anyone who reports using medications listed in Section 4.2 Exclusion Criteria will be asked to stop use of the product for 14 days before the PK testing session.
- Vital signs – The following vital signs will be recorded to verify they are within normal ranges: heart rate, blood pressure, respiration rate.

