Random assignment into study group will occur upon arrival at the PK testing session. Participants will be assigned to one of two study groups – enteric capsules or non-enteric capsules.

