9.2 Sample Size and Randomization

Sample size is based upon previous research published by Loew and colleagues¹ in which six healthy adult males received a single 150mg harpagoside dose through consumption of 600mg *Harpagophytum* extract HF 8858. The C_{max} value was reached within 1.3 hours following dosing and was calculated as 32.2 ng/mL; the half-life of this dose level was 5.6 hours. Given our plan to compare pharmacokinetic parameters between participants who are dosed with enteric versus non-enteric coated capsules, we doubled the sample size used by Loew and colleagues in order to do this comparison. We will collect complete data from 12 participants.

Treatment Assignment Procedures

Group assignment will be linked to the participant identification (PID) number that will be assigned at the start of the PK Testing Session. Study staff responsible for the PK Testing Session will be given the appropriate PID number to use for the participant attending the Testing Session; the PID number will not indicate specifics of the study product assigned to the individual.

All study staff who have direct contact with study participants and/or are involved in data collection or analysis, including the PI and the study biostatistician, will be blinded as to randomization assignment into study group (i.e., enteric or non-enteric capsules). Knowledge of random assignment will remain blinded until all preliminary data reviews and quality checks are completed.

The randomization procedures and assignment list will be the responsibility of [name], DSMB member. She will have no direct involvement with the study participants, data collection, or statistical analysis of the study data.

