Study capsules (i.e., enteric and non-enteric capsules containing HP extract) will be labeled with a product code number; [name] will develop the master list that links the product code number to the specifics of the capsule material. She will send this list to the University of Missouri Healthcare Inpatient Pharmacy which is responsible for preparing the study material. [name] will also generate a list that identifies the product code associated with each participant study code (PID) number; this product/participant study code match will be based on the randomization list. Study staff who prepare the dosing of product to be given to each participant will only know the match of participant study identification code and product code numbers and will not know the study product capsule type (i.e., enteric or non-enteric). Study staff who are working directly with study participants and study data will only know the participant study identification code for an individual. [name] will be authorized to break the blinding process as needed to evaluate SAE and/or Unanticipated Problems.

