9.3 Definition of Populations

The PK Study will continue until complete data over the 24-hour period following dosing are collected from 12 participants. Analyses will be conducted on the data collected from these participants. Comparisons between values obtained from participants who received the dose of HP extract in the enteric coated capsules versus data from those who received HP extract in non-enteric coated capsules (6 in each group) will be compared.

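### Does the promise of arms balanced by sex fail because only the Précis states it?

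*Protocol*

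**What the plan says.** The Précis (Sample Size and Population) puts six participants on enteric and six on non-enteric capsules, and adds: "We will balance both arms of the study with regards to sex (6 male and 6 female". Sex balance is not mentioned again.

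Section 3 says that equal numbers go to each capsule type. Its paragraph on randomization, blinding and stratification says only "Participants will be randomized to receive HP extract in either enteric coated or non-enteric coated capsules" and names no stratification factor. Section 6.2.2 fixes the timing: "Random assignment into study group will occur upon arrival at the PK testing session". Section 9.2 gives the mechanism, "Group assignment will be linked to the participant identification (PID) number that will be assigned at the start of the PK Testing Session", and says of the link between product code and participant that "this product/participant study code match will be based on the randomization list". A DSMB member is responsible for both the randomization procedures and the list.

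Gender is collected at screening (Section 6.2.1): "The survey will include items to record demographic information needed to describe the study sample (e.g., age, gender, race and ethnicity".

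On numbers, Section 9.2 states "We will collect complete data from 12 participants". Section 9.3 states "The PK Study will continue until complete data over the 24-hour period following dosing are collected from 12 participants" and then takes six in each group for the capsule comparison.

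**The concern.** A balance property is stated in the summary, but the sections that describe how participants are assigned do not repeat it. Someone building the list from Sections 9.2 and 9.3 alone would find no sex stratum, no recruitment quota by sex, and no rule that a replacement takes the arm and sex of the person replaced. The parenthesis adds to the doubt: attached to both arms, six men and six women could be read as twelve per arm, which does not fit a total of 12.

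The stake would be the secondary objective, the comparison of enteric with non-enteric capsules. It is a between-participant comparison at 6 against 6, so if exposure differs by sex, an uneven split mixes a sex effect into the capsule effect. An analysis plan cannot restore balance after enrolment. The primary objective, describing the pharmacokinetics, does not depend on balance between the arms.

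**Working it through.** **Sample size.** Section 9.2 doubles the six volunteers of the cited study: 2 × 6 = 12, six per arm. This reproduces.

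**Reading the parenthesis.** Six men and six women make 12, the whole trial. With six per arm, balance by sex in both arms can only be 3 men + 3 women in each. The sentence has one workable meaning.

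**If the arm-balance half of the sentence were ignored.** Assume exactly 6 men and 6 women, a fixed 6:6 list without sex strata, and no dropout. There are C(12,6) = 924 equally likely allocations:

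| Split of the men between arms | Count | Probability |
|---|---|---|
| 3:3 | C(6,3)² = 400 | 43% |
| 4:2 | 2 × 15 × 15 = 450 | 49% |
| 5:1 | 2 × 6 × 6 = 72 | 8% |
| 6:0 | 2 | 0.2% |

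So 850/924 = 92% are 4:2 or better and 74/924 = 8% are 5:1 or worse.

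**What an imbalance would do.** The protocol gives no sex effect on exposure. Assume that exposure differs between the sexes by a ratio R of 1.25 to 1.5. With m1 and m2 men in the two arms, the capsule ratio shifts by R^((m1 − m2)/6):

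- 4 against 2: R^(1/3) = 1.08 to 1.14
- 5 against 1: R^(2/3) = 1.16 to 1.31

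For scale, assume a between-participant coefficient of variation of 30% to 50% (also not in the protocol). The log-scale SD is √ln(1 + CV²) = 0.294 to 0.472. The standard error at 6 against 6 is SD × √(1/6 + 1/6) = 0.170 to 0.273. With t = 2.228 on 10 degrees of freedom, the 95% interval extends by a factor of 1.46 to 1.84 either side of the estimated ratio. The 4:2 shift lies well inside that.

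**Completers per arm.** Suppose the list is 6:6 and replacements fall 50:50 by arm instead of in the vacated arm. The probability of ending with 6:6 completers is then 89%, 76% or 60% at assumed non-completion of 2%, 5% or 10%. A 7:5 outcome changes the standard error by √[(1/7 + 1/5)/(1/6 + 1/6)] = 1.014, a 1.4% increase.

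**If the text is followed.** Allocate the six men 3:3 and the six women 3:3, and fill any vacated slot with a participant of the same sex in the same arm. Each arm then ends with 3 men, 3 women and six completers with certainty, and the total stays 12.

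**Does any section prevent this?** No. Gender is known from screening, before assignment. Under Section 9.2, staff are handed the PID for the particular person attending, which is compatible with a separate PID series for each sex. Blinding to capsule type does not stop the list holder from reissuing a vacated slot. Section 6.2.1 says that gender helps describe the sample but does not confine it to that use.

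**The case for a change.** The strongest case for a change is that stratification and quotas act before and during enrolment, so a later analysis plan cannot supply them. The protocol has a section devoted to randomization that omits the property its summary promises. Without a quota, even the starting point of six men is uncertain: exactly 6 men among 12 has probability 23%, 18% or 8% at an assumed male share of 50%, 40% or 30%. The list holder has no direct involvement with participants or data, and staff in contact with participants or handling data are blinded, so an imbalance between the arms could go unnoticed until unblinding.

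Part of this stands. The sex rule does appear only once, its parenthesis is loosely placed, and Section 9.2 would have been the natural place to repeat it. The rest depends on someone disregarding the Précis. Those quota probabilities suppose that no one acts on the stated six men and six women. The list holder sits on the DSMB, which under Section 10.3.5 reviews the study protocol, so there is no reason to think that this person sees only Sections 9.2 and 9.3. Nor is the list holder the only one who can know the capsule types: Section 9.2 also sends the master list to the pharmacy. Strata, blocks and replacement slots are commonly set out in a randomization plan or an SAP, and neither is at hand here.

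**Conclusion.** No change to the plan follows. The Précis is operative protocol text and states both the quota and the balance. It has one reading that fits six per arm, and no other section contradicts it. Silence elsewhere is a gap that whoever builds the list fills by following the Précis. The Précis, Section 3 and Section 9.3 agree on equal arms of six, so continuing to 12 completers is naturally read as completing those two sets.

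The 43% chance of exact sex balance and the 89%, 76% and 60% chances of 6:6 completers describe a trial that departs from its own text. Even then the cost is limited: 92% of allocations would be 4:2 or better, a 4:2 split would move the capsule ratio by a factor of 1.08 to 1.14 under an assumed sex ratio of 1.25 to 1.5, and a 7:5 split of completers costs 1.4% in standard error. Under randomization such an imbalance is chance variation, not a systematic bias. The sex ratio, coefficient of variation, male share and non-completion rates are all assumptions, since the protocol gives none of them. Wording the Précis as three men and three women per arm and repeating it in Section 9.2 would be editorial tidying and would alter neither the design nor the analysis.

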1. STUDY OBJECTIVES

1.1 Primary Objective

To determine bioavailability and pharmacokinetic properties of product markers after oral consumption of a daily dose of *H. procumbens* (i.e., capsules containing a total amount of extract yielding 100mg harpagoside) in patients with knee osteoarthritis. We hypothesize that the pharmacokinetic properties of the *H. procumbens* aqueous-ethanolic extract as described in US Patent 6,280,737 B1 (example 2), will resemble the results obtained with healthy subjects without osteoarthritis, as reported by Loew et al.¹

1.2 Secondary Objectives

The secondary objective of the study is to compare the bioavailability and pharmacokinetic properties after dosing with an enteric coated capsule to changes found after dosing with a non-enteric coated capsule. We hypothesize the C_{max} , t_{max} , and AUC values for product markers will be enhanced by the cellulose (enteric) encapsulation.

2. BACKGROUND AND RATIONALE

2.1 Background on Condition, Disease, or Other Primary Study Focus

Musculoskeletal conditions represent a major source of pain, loss of function, and health care expenditure that costs Americans billions of dollars, yearly. Clinical research has provided evidence for safety and efficacy of the botanical dietary supplement *Harpagophytum procumbens* (*H. procumbens* or Devil's Claw) for many patients suffering from arthritis and chronic low back pain.⁴⁻¹⁰ The variability in the natural products, however, and lack of a well-defined biological signature necessitate additional exploratory studies with well-characterized products, so that subsequent clinical studies of appropriate methodological rigor can be conducted.^{8,10-17} For osteoarthritis (OA), there are currently no biomarkers qualified as surrogate clinical endpoints, and assessment of the efficacy of disease-modifying osteoarthritis drugs (DMOADs) in patients has provided only sparse understanding of the relationship between biomarkers and the effects of the medication.¹⁸⁻²⁰ These shortcomings may be due to the complex nature of deteriorating diarthrodial joints and the symptoms experienced by patients.

The study will use a well-characterized *H. procumbens* extract (HP extract) to assess the bioavailability and pharmacokinetic properties of product markers after oral consumption of a daily dose of *H. procumbens* (i.e., capsules containing a total amount of extract yielding 100mg harpagoside). Completion of this study will ensure that future clinical trials can be conducted with the methodological rigor and outcome measures needed to appropriately evaluate the effectiveness of this *H. procumbens* product.

